All participants will be patients whose response to prior therapies has been partially successful, but limited, and whose disease state and current course represent risk for eventual refractoriness but who have not yet become fully refractory. As defined in detail below, under International Headache Society (IHS) guidelines all of these patients will be classified as "episodic" or acute. None will be classified as "chronic." In assessing the effectiveness of the SNS CVS-M Device, the Pivotal Study will consider both (1) a patient's number of Headaches as well as (2) the severity of each and of all of those Headaches. The current design path involves evaluating those two disease factors both separately and on a blended basis. The primary endpoint is based on a traditional measure with which both the FDA and the medical profession are quite familiar: outcomes data collected during the Treatment Period vs. baseline data from the Pre-Treatment Baseline Period, focusing on comparative number of Migraine Headache Days. Additionally, the concept of blending those two disease measures into one quantitative assessment will be introduced: a Total Monthly Headache Pain score. As defined below, that Monthly measure will be the cumulative maximal Headache Pain Scores for all Headache Days (days on which the patient's Headache Pain level is one or higher on an eleven-point scale) during the Month in question – thus, a quantitative indication of Total Monthly Headache Pain. Study data can (and will) also be analyzed using other metrics, as described below.

For the Pivotal Study to demonstrate efficacy from SNS CVS-M Device treatments, the therapy must provide prophylactic and/or abortive-response benefits for patients. (However, for clarity, CVS-M is viewed as providing adjunctive prophylactic therapy.) Experience from IRB-approved pilot studies indicates that beneficial preventive effects and diminished incidence and severity of Headaches are achieved through daily CVS-M treatments, but not necessarily beginning immediately upon the first treatment. For that reason, patients will be treated for three Months and only the Headache burden during the last Month will be used for comparison with baseline data.

Description of the Treatment Paradigm and Study

1) Intended Use/Indication for Use

- **Intended Use:** The SNS CVS-M Device is intended to stimulate the vestibular system via external ear canals using controlled thermal waveforms.

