- Indication for Use: The SNS CVS-M Device is specifically indicated to treat episodic Migraine Headache pain.

2) Patient Selection Criteria Pre-Treatment Data

In working with and through their respective designated Pivotal Study assistant(s)/coordinator(s), the Investigators will identify and screen potential participants, all of whom will have previously been diagnosed as episodic migraine patients. The Investigators will review the patients' medical records to select those individuals whom they identify as meeting the inclusion criteria for participating in the Study.

- **Inclusion Criteria:** Each participant must have a Pre-Treatment History that, when initially screened by a Pivotal Study Investigator or designee, documents that she/he meets all elements of the following:
 - The patient must have been diagnosed with episodic Migraine Headache at least six months prior to entering into the Study, consistent with the International Headache Classification of Headache Disorders-II (ICHD-II) guidelines.
 - The patient must have a history of at least three consecutive months of stable Migraine Headaches prior to entering the Study. The patients will not have had changes in medication usage for the three Months leading up to the Study, nor will they introduce new medications during the Study period. Patients will satisfy these criteria: On a Monthly basis, at least four, and not more than a total of fourteen (4-14), Headache Days of which between four and fourteen (4-14) are Migraine Headache Days.
 - The patient must not have failed on more than two classes of properly administered prophylactic pharmaceutical therapies for migraine headache. The patient may be on a single migraine prophylactic as long as the dosage has not been altered within three months of starting the Study and the dosage must not be altered for the duration of the Study;
 - The Investigator must have confidence in the patient's ability to reliably use the CVS-M Device and promptly complete the Daily Headache Diary forms and promptly return them to the Study coordinator. That Daily Headache Diary will be completed from the beginning of the Pre-Treatment Baseline Period through the end of the Pivotal Study. It is described more fully below and in the Definitions section at the end of this document.
- **Exclusion Criteria**: Individuals who:
 - o are pregnant
 - have a history of cardiovascular disease
 - work night shifts
 - o have been diagnosed with vestibular migraine

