 - o have been diagnosed with migraine with aura
 - have menstrual migraine exclusively

- have been diagnosed with post-traumatic migraine
- o have a history of unstable mood disorder or unstable anxiety disorder
- o use a hearing aid
- have a cochlear implant
- have chronic tinnitus
- have temporomandibular joint disease
- have been diagnosed with traumatic brain injury
- o have been diagnosed with neurological disease other than Headaches
- o have a diagnosed vestibular dysfunction
- o abuse alcohol or other drugs
- are experiencing medication overuse Headaches (individuals with respect to whom the Investigator is concerned that analgesic abuse is involved based on the ICHD-II guidelines).
- o are less than 18 years old or greater than 65 years old
- $\circ~$ have had eye surgery within the previous three months or ear surgery within the previous six months
- have active ear infections or a perforated tympanic membrane
- have participated in another clinical trial within the last 30 days or are currently enrolled in another clinical trial
- are using Botox treatments for migraines.
- Though not excluded, patients taking anti-histamines or anti-nausea drugs will be encouraged not to take such medications within four hours prior to a CVS-M treatment. The Investigator should review other medications taken by the patient with properties that mimic anti-nausea or antidizziness drugs as these may reduce responsiveness of the vestibular system to caloric stimulation. Such medications should also be avoided within four hours prior to a CVS-M treatment.

• Withdrawal Criteria

- Subjects must be withdrawn from the clinical trial if any of the following events occur:
 - A subject does not continue to meet Inclusion/Exclusion criteria.
 - A subject is significantly non-compliant with the requirements of the protocol (Investigator decision).
 - A subject becomes pregnant during the trial as evidenced by a positive pregnancy test.
 - The subject develops an illness (Adverse Event) that would interfere with his/her continued participation.
 - The subject is unwilling to continue due to lack of efficacy.

- The subject withdraws his/her consent.
- The Investigator feels that it is the subject's best interest to be withdrawn.
- Scion Neurostim discontinues the study or has achieved the targeted enrollment.

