If the subject is discontinued from the participation in the study for any reason, the Investigator must make every effort to perform all evaluations for the final visit and document the reasons for discontinuation.

• Concomitant Medications

- The use of acute abortive medications for the symptomatic treatment of migraine headache will be allowed during the clinical trial. Subjects may use their usual acute abortive medications, and medications should not be changed during the clinical trial. A Treated Headache will be a Migraine Headache for which a patient has taken an acute abortive medication.
- The patient may be on a single migraine prophylactic as long as the dosage has not been altered within three months of starting the Study and the dosage must not be altered for the duration of the Study. The patient must not have failed on more than two classes of properly administered prophylactic pharmaceutical therapies for migraine headache. Prophylactic medications used to treat other medical conditions may be used, at the Investigator's discretion, if the subject is taking a stable dose for at least three months prior to screening and continues throughout the study.

3) Pivotal Study Size; Randomization

The design size contemplates enrolling up to eighty (80) patients who will successfully follow through to completion of their participation in the Pivotal Study. Half of these patients will be assigned a Treatment Device, and half will be assigned a Placebo Device. Whether a patient is in the treatment arm or placebo arm will be decided randomly based on an assignment within a sealed envelope, which will be opened only by the Pivotal Study coordinator at the relevant Pivotal Study site. The envelopes will be randomized as described below and provided to the participating clinics. A given patient and the Investigator will remain blinded as to the arm to which the patient has been assigned. The assessment of the primary endpoints will be completed by a blinded, central Statistician. The patients will be told, within the informed consent document, of the existence of a placebo arm.

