Block randomization with a block size of four (4) will be used at each site. Each site will receive sets of well-shuffled envelopes in packets of four. A given packet will be completed before the next packet is opened. Each packet of four will contain two cards specifying that a subject should be in the active treatment arm and two cards specifying the placebo arm. This procedure results in six possible different arrangements, for four patients, of the ordering of treatment and placebo assignments. The unblinded Pivotal Study coordinator will record the patient's designation but will not share the assignment with the patient, Investigator, or Statistician.

4) Pivotal Study Schedule; Subject Enrollment and Activities; Monitoring

The Pivotal Study Period will last one hundred and twelve days, beginning with a Pre-Treatment Baseline Period of one Month (28 days), at the end of which the Investigator will reconfirm the appropriateness of the subject's participation in the Pivotal Study, followed by a Treatment Period of three Months (84 days).

As noted, subjects will be advised that during the Pivotal Study Period they may maintain patterns of usage of approved therapeutic medications that they normally use and that they should not initiate new medications, medicating patterns or other interventions. Accommodations for rescue medications will be made, using pharmaceuticals from an approved list developed by the Investigators.

Potential participants will be required to keep a Daily Headache Diary throughout the Pivotal Study Period and, *inter alia*, to document times of CVS-M treatments. They will enter the Daily Headache Diary information using a computer-based system.

The phases and activities of the Pivotal Study are listed below:

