50%	10%	80%	40
55%	10%	80%	32

The ONSTIM (occipital nerve stimulator) study (Saper et al.) recorded a placebo (preset stimulation) efficacy of 6% and a responder rate (reduction of 50% or more in headache frequency) of 39%. Results from the PREMICE study (Cefaly, supraorbital transcutaneous neurostimulation) cited by Lambert listed a placebo efficacy of 12.1% and a responder rate of 37%. Both studies evaluated between 60-70 patients. Therefore, the range of 10-15% for placebo efficacy is felt to be relatively conservative as compared with other recent studies involving neuromodulation devices addressing Migraine Headache. The assumed efficacy rate range for the CVS Device is based on non-statistically significant observations in the two previous Migraine pilot studies. We therefore conclude that a total Study size of 80 patients is likely to be sufficient for the most probable outcomes, as that number exceeds the minimum in the table above for the most likely treatment and placebo efficacy cases. For comparison, Topiramate (Topamax) used as a prophylactic migraine treatment reports responder rates in the 37-54% range and a placebo response in the low 20% range. Therefore CVS-M responder rates in the 45-55% range would be clinically meaningful.

• **Cohort size**: Each of the sites will enroll subjects with an overall goal of 80 patients. Once up to 80 subjects have completed the Pivotal Study successfully, enrollment in the Pivotal Study will be stopped (at least temporarily) and the data will be analyzed and summarized. Using expected levels of efficacy for the Treatment and Placebo Devices, this cohort size will likely be more than adequate to demonstrate statistical significance and reject the null hypothesis. The cohort size is also expected to be adequate to establish the low rate of unanticipated adverse events associated with usage of the Device. The Sponsor may choose to extend the Study, with IRB approval, should it be necessary to increase the patient cohort size.

Summary of analytical methodologies to be used for additional safety assessments and for the Secondary Endpoints:

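### Read literally, a randomised patient who starts a new drug or changes a prophylactic dose must leave the trial, so her Month 3 outcome can be lost for a reason plausibly tied to poor control

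*Combined protocol and SAP*

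**What the plan says.** All references are to the combined protocol and SAP.

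- **Section 2, Inclusion Criteria.** Two elements look forward rather than back. Patients will have had stable medication for three Months, "nor will they introduce new medications during the Study period". For a patient on a single prophylactic, "the dosage must not be altered for the duration of the Study".
- **Section 2, Withdrawal Criteria.** The list is mandatory and concerns withdrawal from the trial, not only from the device. Its first trigger is "A subject does not continue to meet Inclusion/Exclusion criteria". Investigator judgement is attached to the next trigger, significant non-compliance, but not to this one.
- **After discontinuation (same section).** "the Investigator must make every effort to perform all evaluations for the final visit and document the reasons for discontinuation".
- **Section 4.** Patients are advised that "they should not initiate new medications, medicating patterns or other interventions". The next sentence reads "Accommodations for rescue medications will be made, using pharmaceuticals from an approved list developed by the Investigators".
- **Background.** "only the Headache burden during the last Month will be used for comparison with baseline data". The Definitions make the daily diary the main instrument for the primary and secondary endpoints.
- **Section 9, Cohort size.** "Once up to 80 subjects have completed the Pivotal Study successfully, enrollment in the Pivotal Study will be stopped".

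The document defines no analysis population and gives no missing-data rule.

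**The concern.** The patient who adds or raises a headache drug during treatment may well be the patient whose migraine is not controlled. If that event removes her from the trial before or during the third Month, whether her outcome is seen can depend on what it would have been. Completers are then a selected group, and the selection can differ between arms.

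Enrolling until the completer target is met replaces the numbers but does not restore the randomised comparison. Because only the third Month counts, an earlier exit leaves no usable primary outcome. If the diary stops at exit, no later analysis can recover it or show which way the bias ran. Sites may also read the rule differently, one withdrawing the patient and another logging a deviation, which would make the loss depend on site.

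**Working it through.** **Step 1: does the text lead to withdrawal?** The no-new-medication clause and the fixed-dose clause are both written as inclusion elements and both run through the study. The withdrawal list removes anyone who stops meeting those elements. So, literally, a post-randomisation drug start or dose change leads to mandatory exit.

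**Step 2: is the outcome then lost?** The only stated duty after exit is the final-visit evaluations. Section 4(iv) lists those as the quality-of-life and cognition exam, the vestibular test, the usability questionnaire and collection of device data. None of them supplies a 28-day diary.

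**Step 3: check the plan's own table.** Section 9 bases sample size on the proportion with a 50% or greater reduction in Migraine Headache Days, two-sided, 80% power. Alpha is not stated; 0.05 is assumed. With p̄ = (p1 + p2)/2,

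n per arm = [1.960·√(2p̄(1−p̄)) + 0.842·√(p1(1−p1) + p2(1−p2))]² / (p1−p2)².

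For 45% v 15%, p̄ = 0.30 and n = 35.4, rounded up to 36 per arm, total 72, as printed. The same formula gives 54, 44, 50, 40 and 32 for the other rows, all as printed. This supports the assumed alpha. The table is not affected by this point.

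**Step 4: illustrate the size.** Inputs: the table's most cautious row (45% v 15%), 40 completers per arm (half of 80), Pearson chi-square without continuity correction. The number withdrawn per arm, k, is an assumption, because the documents give no rate. The withdrawn patients are added to the 40 completers, since they do not count toward the 80.

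Base case: 0.45 × 40 = 18 and 0.15 × 40 = 6, so 18/40 v 6/40, 30.0 points, p=0.0034.

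| k per arm | Outcome assigned to the withdrawn | Active | Placebo | Difference (points) | p |
|---|---|---|---|---|---|
| 2 | all non-responders | 18/42 | 6/42 | 28.6 | 0.0038 |
| 2 | worst for device | 18/42 | 8/42 | 23.8 | 0.0183 |
| 2 | best for device | 20/42 | 6/42 | 33.3 | 0.00095 |
| 3 | worst for device | 18/43 | 9/43 | 20.9 | 0.0365 |
| 4 | all non-responders | 18/44 | 6/44 | 27.3 | 0.0041 |
| 4 | worst for device | 18/44 | 10/44 | 18.2 | 0.0671 |
| 4 | best for device | 22/44 | 6/44 | 36.4 | 0.00025 |

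Worst for device means that every withdrawn active patient is a non-responder and every withdrawn placebo patient a responder; best is the reverse.

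**Step 5: selection with equal loss rates.** If a fraction w of non-responders is withdrawn in both arms, the completer response rate is p / [p + (1−p)(1−w)]. With w = 0.20 (assumed), active is 0.45/(0.45 + 0.55 × 0.80) = 50.6% and placebo is 0.15/(0.15 + 0.85 × 0.80) = 18.1%. The apparent difference is 32.5 points against a true 30.

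**The case against.** There are five serious points on the other side.

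1. **The literal reading may not be the intended one.** The inclusion list is introduced as a history documented at initial screening, which cannot cover future conduct. Section 4 words the ban as advice, and a breach fits naturally under significant non-compliance, where the Investigator decides. Applying the trigger to every inclusion element would also expel responders: a patient who falls from 6 to 3 Migraine Headache Days no longer meets the 4-to-14 range. This stands as evidence of ambiguity. It does not remove the problem, because the medication clauses expressly name the study period and the trigger carries the criteria forward.

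2. **Some of it is already covered.** The rescue sentence follows the ban directly and is best read as an exception, and diaries are required throughout the study period. Both are fair. But section 2 does not state the exception, and the diary text does not address a withdrawn patient.

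3. **The effect is small under the proposed mechanism.** If the withdrawn are mostly non-responders, little changes. Even if only the active arm loses non-responders, 4 lost gives 18/44 v 6/40 (p=0.009), 8 lost gives 18/48 v 6/40 (p=0.018), and 14 lost gives 18/54 v 6/40 (p=0.044). The case that loses significance needs all four withdrawn placebo patients to be responders, which sits badly with poor control as the cause. This stands and limits the weight of the point.

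4. **It is part of a wider gap.** Withdrawal for lack of efficacy is a more direct route to outcome-related loss, and there is no analysis set for any withdrawal. True, and this fix does not settle that.

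5. **Keeping such patients lets a drug effect into Month 3.** That is a choice about what is estimated in a device tested alongside stable therapy. It is a real cost, and the sensitivity analysis is there to address it.

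**Conclusion.** The concern holds at moderate weight. Followed as written, the plan can remove randomised patients for a reason plausibly related to outcome and leave no Month 3 diary for them. The link to poor control is clinical inference; the documents do not state it.

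The size and direction of any bias are unknown. Under the assumed base case and two-sided 0.05, counting the withdrawn as non-responders moves the 30-point difference by less than 3 points at up to 4 per arm. Only the extreme worst case loses significance, first at 4 per arm. This is therefore not a prediction that the trial would fail. It is a should-fix matter because diary data not collected cannot be recovered afterwards.

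**What to change.** 1. In section 2, Withdrawal Criteria, add two sentences. First, use of a listed rescue drug does not breach eligibility. Second, any other medication start or dose change after randomisation is recorded as a protocol deviation (drug, date, reason) and is not by itself a reason to stop the diary, which continues through Month 3.
2. Keep the ban as an instruction to patients.
3. Report medication starts and changes by arm.
4. Add one sensitivity analysis that counts as a non-responder any patient who started or changed a migraine drug, other than permitted listed rescue, before or in Month 3.

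The cost is two sentences, one table and one analysis; the computer-based diary is already in use. The downside is that some Month 3 outcomes will include the effect of an added drug, which item 4 addresses. The rescue sentence alone would be only a clarification; the substance lies in continuing the diary.

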July 24, 2014

SCION NEUROSTIM, LLC:

PIVOTAL MIGRAINE STUDY

Title: A Non-Invasive Neuromodulation Device for Treatment of Migraine Headache

Background

This "Pivotal Study" is a multi-center, triple-blinded, placebo-controlled, randomized Pivotal Study for adjunctive prophylactic treatment of episodic migraine headache using a caloric vestibular stimulation (CVS) Device developed by Scion NeuroStim, LLC (SNS). This Study has been reviewed by the FDA and is classified as NSR (nonsignificant risk).

Set forth at the end of this document is an alphabetical listing of the various capitalized definitions and terms that are used throughout the document, and attached are various forms that will be used to conduct and collect data during the Pivotal Study.

Efficacy of neuromodulation therapy for migraines is reasonably well-established. Traditionally, however, neuromodulation, especially when accomplished through an expensive, surgically implanted device, has been available only as a treatment of last resort -- to be used (and covered by health insurance) if, but only after, patients have failed all other interventions, principally pharmaceuticals. Typically, patients receive neuromodulation for migraines only after they are refractory or close to being refractory. SNS envisions changing that paradigm, providing effective early interventions and thereby improving outcomes for migraine patients. The CVS-M Device is non-invasive and utilizes the same underlying mode of neural modulation (activation of the vestibular nuclei in the brainstem) that for a century has been well-understood by the medical profession and has been used safely via caloric irrigators for diagnostic purposes -- in ENT practices to assess balance and in the ER to assess brain function. The SNS Device is relatively inexpensive and easy to operate; it can be used safely at home by a patient under the supervision of a prescribing physician. Through availability and use of the SNS CVS-M Device, prophylactic neuromodulation therapy for migraines can become an inexpensive and early, rather than an expensive and belated, therapeutic option.

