Experience with pilot study patients as well as a theoretical understanding of CVS indicates that the SNS Device likely can effectively treat both episodic and chronic migraine patients, but this Pivotal Study will focus on only episodic patients. The Investigators at the Pivotal Study sites will identify, select and treat a carefully defined population of individuals who are current patients with an established history of episodic migraines and who have substantial monthly migraine days and pain, but who have not

yet become refractory to all conventional treatments. CVS-M Device treatments will be evaluated as a therapy to be used alongside the therapies that are currently being utilized by participating patients (i.e., as an adjuvant), again underscoring the potential advantages of earlier neuromodulation therapy intervention. Limiting participation to patients who meet the carefully selected qualifications will simplify how the Pivotal Study is conducted and how the results are evaluated.

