- The waveform schedule for placebo treatment patients will consist of turning on the cooling fans and leaving the earpieces unpowered for a ~4-minute period.
- The earpiece tips will be covered with EVA rubber to prevent cooling of the ear canal by the metallic earpieces.

The Placebo Device will look identical to the Treatment Device and *will* show, on its screen, a time-varying waveform similar to that for an active treatment. The y-axis of the plot will be labeled "stimulation intensity" and will not list temperature values (the same will be true for the Treatment Device). A patient receiving a placebo treatment will have the sensation of the earpieces creating some pressure in the ear canals and may feel the earpieces warm up to body temperature. Placebo patients will not undergo material caloric vestibular stimulation since no temperature gradient will be created across the horizontal semicircular canal. (The threshold for therapeutic benefit using CVS has not been established, but even small temperature changes can result in nystagmus (Sedjawidata et al. & Vesterhauge et al.).) The term "CVS" will not be used in describing the Device to any patient and no reference to caloric stimulation will be made. The Device will be referred to as a neuromodulation device and the specific mechanism of action will not be disclosed to patients.

All patients will be told that they may or may not benefit from the Device in terms of

pain reduction and that, further, the point in the 3-month treatment period at which a change may be noticed is unknown and may vary from patient-to-patient – i.e., the treatment duration necessary for a potential reduction in pain is unknown for any particular individual. Patients will be told that they may or may not sense slight pressure from the earpieces, a warming or cooling sensation, or slight nausea or dizziness, especially at the end of the treatment session. At the conclusion of the Treatment Period, patients will be asked to identify which arm they believe they entered (active treatment or placebo).

6) Safety; Vestibular System Examination and Monitoring

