CVS has been used extensively and safely in the practice of medicine since its discovery more than a century ago by [name], a discovery for which he received the Nobel Prize in Physiology/Medicine in 1914. There have been no reports in the literature of adverse events or significant negative side effects associated with CVS. The side effect profile from use of the CVS-M Device is expected to be the same as that associated with diagnostic CVS procedures.

CVS-M acts on the central nervous system via the vestibular organs. This mechanism is distinctly different from most forms of neurostimulation that involve either electrical currents applied directly to a target nerve or region (implanted neurostimulators) or a diffuse current to larger areas of the cortex (TMS, CES, tDCS). CVS is non-invasive and easily employed. The SNS CVS-M Device enables its therapeutic use and utility by controlling thermal induction and providing safeguards that ensure treatments remain firmly within parameters established by the supervising physician.

The Berg Balance test (Berg et al.) is well-established and widely used in clinical settings to asses a person's static and dynamic balance abilities. *Inter alia*, the Test is used to quantify clinical improvement or deterioration in patients -- from evaluation of "normals" to assessment of individuals with a wide range of balance impediments. The long form Test consists of 14 balance- related tasks ranging from standing up from a sitting position to standing on one foot. Each task is graded from 0 - 4, and the final measure is the sum from all elements of the Test:

- 41-56 = low risk of fall
- 21-40 = medium risk of fall
- 0-20 = high risk of fall

The Berg Balance test will provide a consistent and easily administered, task-based scheme for identification and quantification of deterioration, if any, of a subject's balance that could be associated with use of the CVS-M Device. The local clinical coordinators will undergo training on administration of the Berg test prior to the Study. Abnormal findings with the Berg test may lead to a more extensive vestibular assessment evaluation. No unexpected side effects, nor any adverse events, have occurred in prior studies utilizing the CVS-M Device.

7) Pivotal Study Endpoints

• Primary Efficacy Endpoint for the Pivotal Study

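### Patients who used this device in the sponsor's pilot studies can be enrolled once 30 days have passed, although the patient blind depends on not knowing the stimulus (low severity)

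*Combined protocol and SAP*

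**What the plan says.** **Eligibility.** Section 2 (Patient Selection Criteria), Exclusion Criteria, removes people who "have participated in another clinical trial within the last 30 days or are currently enrolled in another clinical trial". This is a general rule and is not specific to the device. No criterion in section 2 mentions earlier use of the device or earlier caloric stimulation. The nearest one removes people who "have a diagnosed vestibular dysfunction", which concerns a diagnosis and not exposure.

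**Former users exist.** Section 9 says the response rate assumed for the device is "based on non-statistically significant observations in the two previous Migraine pilot studies". Section 6 states that no unexpected side effects or adverse events "have occurred in prior studies utilizing the CVS-M Device". The Background and the safety endpoint in section 7 also draw on pilot patients treated with the device.

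**The blind.** Section 5 keeps the term CVS and any mention of caloric stimulation away from patients: "The Device will be referred to as a neuromodulation device and the specific mechanism of action will not be disclosed to patients". Patients are told that they may or may not feel pressure, warming, cooling, or slight nausea or dizziness. The same section sets active sessions at about 19 minutes, with one ear warmed to 42 °C and the other cooled to 17 °C. Placebo sessions last about 4 minutes with the fans on and the earpieces unpowered. Patients guess their arm at the end of treatment, but no analysis of the guess is described.

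**The outcome.** Under Definitions, the Daily Headache Diary is the main instrument for the endpoints, and the patient decides whether a headache counts as a migraine.

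**The concern.** Withholding the mechanism and describing sensations neutrally can protect a patient who has nothing to compare the session with. They protect much less well against someone who has already treated themselves with the device and can set a short, unpowered session against what they remember.

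Migraine Headache Days, the 50% responder rate, Total Monthly Headache Pain and Treated Headaches all rest on the diary. A patient who knows the arm can bring expectation (active) or disappointment (placebo) into these outcomes, and both push the difference between arms in favour of the device. As the plan stands, former users are not listed as something to record, so the trial could neither count them nor show that its result holds without them.

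**Working it through.** **1. Can a former user get in?**

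| Provision | Effect on a pilot participant |
|---|---|
| 30-day rule (section 2) | Excluded only until 30 days have passed |
| Stability rule (section 2) | Names medication changes over three months, not device use |
| Withdrawal Criteria (section 2) | No provision on earlier use |
| Screening vestibular test (Definitions) | The Berg Balance test, which does not detect earlier exposure |
| Investigator's reconfirmation (Definitions) | Discretion only; earlier use is not named |

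If the 30 days are counted at screening, the 28-day baseline puts the first session at least 30 + 28 = 58 days after the pilot. That is no safeguard against remembering the sensation.

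**2. The plan's own sample size.** Section 9 gives total sizes of 72, 54, 44, 50, 40 and 32 at 80% power. Alpha is not stated, so two-sided 0.05 is assumed. The per-arm formula with pooled variance is

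n = [1.960·√(2p̄(1−p̄)) + 0.842·√(p₁(1−p₁) + p₂(1−p₂))]² / (p₁−p₂)²

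For 45% against 15%, p̄ = 0.30, so n = [1.960·√0.42 + 0.842·√0.375]² / 0.09 = 35.4. This rounds up to 36 per arm, 72 in total. The same formula reproduces all six rows, so the point does not rest on an error in the table.

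**3. How large could the bias be?** The illustration uses the responder rate, the metric on which section 9 sizes the trial. Assumptions, none of them from the documents:
- there is no true effect, and the true responder rate p is 10% or 15% in both arms (the plan's placebo range);
- k former users per arm of 40 all identify their arm;
- their responder probability moves by s = 0.1 to 0.3, up on active and down on placebo, but not below zero.

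With f = k/40, the expected rates are p + f·s on active and p − f·min(s, p) on placebo. For k = 4, s = 0.3 and p = 0.15:
- active: 0.15 + 0.10 × 0.30 = 0.180
- placebo: 0.15 − 0.10 × 0.15 = 0.135
- spurious difference: 4.5 percentage points

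The rejection rates below come from exact binomial enumeration of the Pearson chi-square test.

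| k per arm | Share of arm | Spurious difference (s = 0.3, p = 15%) | Rejection rate, all s and both p |
|---|---|---|---|
| 0 | 0% | 0 | 5.4–5.9% |
| 2 | 5% | 2.25 points | 5.5–6.8% |
| 4 | 10% | 4.5 points | 6.1–9.7% |
| 8 | 20% | 9.0 points | 8.3–20.8% |

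The upper ends belong to p = 10% and should be read against 5.9%. The lower ends belong to p = 15% and should be read against 5.4%. The planned difference is 30 (45 − 15) to 45 (55 − 10) points.

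**The case against.** The strongest reply is that the documents do not show that any former user would enrol. They give neither the number of pilot patients nor their sites. The Background suggests that pilot experience bore on chronic as well as episodic migraine, and chronic patients are ineligible here. Pilot waveforms and session lengths are not described, so recognition is an inference. Investigators review medical records, and the Headache History Questionnaire is not shown, so earlier use may already come up. The contrast between the two kinds of session could also affect naive patients, which is a wider matter than this one. All of this stands, and it limits the size of the point. It does not close the gap, because no written rule keeps former users out.

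A reader might infer several stronger things that the documents do not support:

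- **That people with a past diagnostic caloric test are a comparable threat, or must wait 30 days.** The Background says this mode of stimulation "has been used safely via caloric irrigators for diagnostic purposes", so such patients may well be among the candidates. The 30-day rule covers trial participation only, so no wait applies to them. Recognising the arm from one irrigator test is speculative: the device delivers simultaneous warm and cold waveforms through earpieces, and the patient would also have to guess that temperature is the active element. Exclusions for vestibular migraine, vestibular dysfunction, other neurological disease, brain injury and chronic tinnitus plausibly remove many people who have been tested.
- **That every efficacy endpoint is patient-reported.** The Quality of Life and Cognition Assessment includes performance tests (Digit-Symbol, Trail Making, word association, face recognition).
- **That pilot patients who did well would be the ones to return.** Nothing in the documents bears on this.

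**Conclusion.** The point holds in a narrow form and is of low severity. As written, a migraine patient who has used this device can be randomised into a trial whose patient blind relies on unfamiliarity with the stimulus. Such a patient is likely, though not certain, to recognise the arm.

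The size cannot be estimated, because the documents give neither the number of former users nor how far their reporting would shift. Two per arm would add at most about one percentage point to the false-positive rate (5.9% to 6.8%). The effect becomes material only with several per arm: up to 9.7% with four and up to 20.8% with eight, under the largest shift considered. These figures are a range under chosen inputs and not a forecast. They assume that every former user identifies the arm, and that former users are equally many in both arms. The case for acting rests on how cheap the remedy is and not on a demonstrated large bias.

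**What to change.** 1. Add to the Exclusion Criteria in section 2: *have previously used the SNS CVS Device, including in a pilot study*. Check candidates against the sponsor's pilot records before randomisation. Do not ask patients about earlier ear-canal temperature procedures, since such a question would hint at the mechanism that section 5 withholds.
2. Do not exclude for earlier diagnostic caloric testing. Note it, before randomisation, from the medical records that Investigators already review under section 2. Pre-specify in section 9 a sensitivity analysis of the primary comparison without those patients. Records may be incomplete, so this is a check and not a guarantee.

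**Cost.** One exclusion line, a records check and one sensitivity analysis, at the price of a few otherwise eligible patients. The target of 80 completers stays, and because enrolment runs to that target, lost patients can be replaced. At 80, approximate power runs from 84.7% (45% against 15%) to 99.6% (55% against 10%). If 2, 4 or 6 patients were lost and not replaced, power in the least favourable row would be 83.8%, 82.8% or 81.7%, still above the planned 80%.
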